**Table 3 - Dose escalation rule of the modified toxicity probability interval-2 method**

|                                    |    | Number of DLT-evaluable participants |    |    |    |    |    |    |    |    |    |
|------------------------------------|----|--------------------------------------|----|----|----|----|----|----|----|----|----|
|                                    |    | 1                                    | 2  | 3  | 4  | 5  | 6  | 7  | 8  | 9  | 10 |
| Number of dose limiting toxicities | 0  | E                                    | E  | E  | E  | E  | E  | E  | E  | E  | E  |
|                                    | 1  | D                                    | D  | S  | S  | E  | E  | E  | E  | E  | E  |
|                                    | 2  |                                      | DU | D  | D  | D  | S  | S  | S  | E  | E  |
|                                    | 3  |                                      |    | DU | DU | D  | D  | D  | D  | S  | S  |
|                                    | 4  |                                      |    |    | DU | DU | DU | D  | D  | D  | D  |
|                                    | 5  |                                      |    |    |    | DU | DU | DU | DU | DU | D  |
|                                    | 6  |                                      |    |    |    |    | DU | DU | DU | DU | DU |
|                                    | 7  |                                      |    |    |    |    |    | DU | DU | DU | DU |
|                                    | 8  |                                      |    |    |    |    |    |    | DU | DU | DU |
|                                    | 9  |                                      |    |    |    |    |    |    |    | DU | DU |
|                                    | 10 |                                      |    |    |    |    |    |    |    |    | DU |

E: Escalate to the next higher dose, S: Stay at the current dose, D: De-escalate to the next lower dose, DU: De-escalate to the next lower dose and the current dose will never be used again because unacceptable high toxicity.

**Dose limiting toxicity:** The following events occurring during the DLT observation period (21 days of first cycle) are considered as DLT unless due to disease progression or to a cause obviously unrelated to study drugs. Please refer to the list of events as below. Based on the occurrence of DLT and overall assessment of safety data supplemented with data from other SAR444245 studies, the Study Board will determine if the dose of SAR444245 needs to be reduced to ■ µg/kg Q3W or another lower dose level, in agreement with the Sponsor.

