| Concomitant medication              |  | Continuously throughout treatment period |    |                 |                |                |                   |                |                |                              |                |                |   |                                      |                                      |                        |   | See Section 6.8 of master protocol |                                    |
| First subsequent anticancer therapy |  |  |    |                 |                |                |                   |                |                |                              |                |                | X   | X                                    | X                                    | X                      | X   |                                    |                                    |
| Survival status                     |  |  |    |                 |                |                |                   |                |                |                              |                |                |   |                                      |                                      |                        |   | X                                  |                                    |

- a* **Evaluation:** There is no need to perform Cycle 1 Day 1 laboratory assessments that have been performed as part of screening within 3 days prior to first IMP administration. During the study treatment period, all assessments must be performed, and results should be reviewed by the investigator **prior to IMP administration** at that visit. After Cycle 1, samples for laboratory assessments (excluding PK & biomarker) can be collected up to 3 days prior to IMP administration. ICF must be signed before any study-specific procedures are performed and can be signed more than 28 days prior to first IMP administration. Screening time indicates the maximum time frame relative to the first IMP administration in which assessments used to support eligibility are done.
- b* **Cycle:** A treatment cycle is 21 days. See details in Section 6.1 of master protocol for IMP administration. If treatment cycles are adjusted, all procedures except tumor assessment imaging will be completed according to the Cycle number. Tumor assessment imaging will be performed at fixed time points from C1D1 regardless of any treatment delays.

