- i* **Brain imaging:** For participants with no previous history of brain metastases, screening brain imaging will need to be obtained. MRI is the preferred imaging modality however CT is acceptable if an MRI is clinically contraindicated. Patients with asymptomatic brain metastases (ie, no neurological symptoms, no requirements for corticosteroids, and no lesion  $>1.5$  cm) may participate but will require regular imaging of the brain as a site of disease as per protocol tumor assessment schedule. In all other cases, the lesions must be treated. Two additional scans obtained at least 4 weeks apart, should be obtained to document disease stability AFTER local treatment administration to the brain metastases has been completed. If participants receive systemic therapy during these 4 weeks stabilization at the treating physician's discretion, this systemic therapy will be considered as part of prior anti-cancer therapy. Participants with previously treated brain metastases may participate provided they are stable, which is defined as lack of progression on two sets of imaging obtained at least 4 weeks apart. Stability as defined above should be documented prior to the first dose of trial treatment. In addition, any neurologic symptoms must have returned to baseline or resolved, and the participant is not using steroids for at least 14 days prior to study treatment. The screening brain scan may be collected up to 42 days prior to enrollment.
- j* **AE/SAE assessment:** Severity will be graded according to NCI-CTCAE v 5.0, ICANS and cytokine release syndrome (CRS) will be graded using ASTCT criteria integrated with central laboratory cytokine results (1).
- k* Urinalysis using dipstick for glucose, blood, pH, protein, ketones, leukocytes and microscopic examination (if blood or protein is abnormal) will be performed every 4 cycles during the Treatment period and as clinically indicated.
- l* Visit and assessments on C1D3 are only for participants in the safety run-in.
- m* Only for safety run-in participants.
- n* Cetuximab dosing only.

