## 1.5 PHARMACOKINETIC FLOWCHART

### 1.5.1 A2 Cohort

| Cycle                                | Treatment Cycle 1 |                   |          |                   |          | Treatment Cycles 2, 3, 4, 6, 8, 10 + every 4 th cycle thereafter | EOT visit
30 (±7) days
after last IMP
admin |       |
|--------------------------------------|-------------------|-------------------|----------|-------------------|----------|---|--|-------|
|                                      | D1                |                   | D2       | D3 c   | D8       |   |  |       |
| Time after start of SAR444245 dosing | SOI               | EOI               | Any time | Any time          | Any time | SOI   | EOI  |       |
| SAR444245 PK sample                  |                   | P00 b  | P01      |                   |          |   | P00 b                                     |       |
| SAR444245 ADA sample                 | AB00 a |                   |          |                   | AB01     | AB00 a   |  | ABF00 |
| Time after start of dosing cetuximab | SOI               | EOI               | D2       | D3 c   | D8       | SOI   | EOI  |       |
| Cetuximab PK sample                  | SC00 a | SC01 b |          | SC02 a |          | SC00 a   | SC01 b                                    |       |

a Samples collected strictly before start of infusion (SOI).

b EOI samples must be taken at end of infusion (EOI) precisely ±5 minutes.

c Day 3 sampling only for participants in the safety run-in who have a Day 3 visit.

Abbreviations: ADA: anti-drug antibodies; D: day; EOI: end of infusion; EOT: end of treatment; PK: pharmacokinetic; SOI: start of infusion.

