## 4 STUDY DESIGN

### 4.1 OVERALL DESIGN

This substudy will include participants with HNSCC who are treatment-naïve for R/M disease, PD-L1 CPS  $\geq 1$  and will assess SAR444245 combined with pembrolizumab and cetuximab.

Overall, approximately 40 participants will be enrolled and treated at the confirmed safe dose in Cohort A2.

The maximum number of cycles allowed in this Cohort A2 substudy is 35 cycles for SAR444245 and pembrolizumab, and until PD for cetuximab.

**A safety run-in** will confirm the dose of SAR444245 when combined with pembrolizumab and cetuximab in a sample of at least 6 participants. After recruitment of the first 10 participants, enrollment will be paused if a total of at least 6 participants are evaluable for DLT. Safety data for these participants will be reviewed by the Study Board comprising the Investigators or designees participating in the safety run-in part of the trial and the Sponsor clinical team members. DLT-evaluable participants include all participants in the safety run-in part who have been treated and observed for at least 21 days. Any participant who experienced a DLT during the first 21 days will also be DLT-evaluable. If no safety concerns are identified by the Study Board, participant enrollment will continue.

If after recruiting the first 10 participants there are fewer than 6 participants evaluable for DLT, more participants will be enrolled to ensure at least 6 DLT evaluable participants after agreement from Study Board. Participants who are enrolled in the safety run-in and treated at the confirmed safe dose will be included in the total number of participants.

The SAR444245 dose to be confirmed is 24  $\mu\text{g}/\text{kg}$ , administered as an IV infusion over 30 minutes every 3 weeks on Day 1 of each cycle (21 days per cycle). Overall safety monitoring will be performed throughout the study. If recommended by the Study Board, SAR444245 dose may be reduced to ■  $\mu\text{g}/\text{kg}$  or another lower dose level which will be explored following the same process described in the safety run-in for 24  $\mu\text{g}/\text{kg}$  dose level.

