#### **6.5.2 Cycle delay and dose omission**

The treatment window is  $\pm 3$  days for each of the Q3W IMP administrations. The treatment window is  $\pm 1$  day for cetuximab administration on Day 8 and Day 15 of each cycle.

A cycle is deemed to have been delayed if the treatment is administered  $\geq 4$  days beyond the theoretical day of Q3W IMP administration. The participant may receive the next dose after recovery from the toxicity as described in [Section 6.5.3](#). After cycle delayed, such participants may be considered for treatment resumption once the toxicity resolves or improves to Grade 1 or baseline.

Participants may have cycle delay, or dose omission if toxicity occurs and the participant does not recover according to following rules:

- For Q3W IMP administration: If toxicity occurs and the participant does not recover on the day of planned administration; restart of study IMPs could occur only on the initiation of the subsequent cycle.
- For cetuximab Day 8 and Day 15 administration in each cycle: if toxicity occurs and the patient does not recover on the day of planned infusion or within the following 3 days, infusion may be omitted.
- In case of cycle delay or dose omissions for the recovery of toxicity, the following rules should be followed for restart or discontinuation of the treatment:
  - In case of a cycle delay up to 14 days or a dose omission, it is per Investigator's decision to restart the study treatment.
  - After a cycle delay of  $>14$  days and  $\leq 84$  days, or 2 to 4 consecutive dose omissions, it is per Investigator's decision to restart the study treatment or the IMP that is omitted, if a clear benefit from treatment is observed and after consultation with the Sponsor.
  - The study treatment must be permanently discontinued if the cycle delay is longer than 84 days.
  - For any delayed cetuximab treatment, do not repeat the initial dose of 400 mg/m^2. At the restart of cetuximab treatment, all subsequent infusions will be at the appropriate dose level according to [Table 5](#).

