**Table 14 - Populations for analyses**

| Population    | Description   |
|---------------|---|
| DLT-evaluable | DLT-evaluable population include all participants in safety run-in part who have been treated and observed for least 21 days. Any participants who have experienced a DLT during DLT observation period will also be DLT-evaluable. |

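### In the Cohort A2 safety run-in, the ±3-day window for Cycle 2 Day 1 permits a second SAR444245 and pembrolizumab dose on Days 19-21, before the 21-day DLT period ends (minor; cheap to close)

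*Protocol*

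**What the plan says.** All references are to the Cohort A2 substudy.

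- **DLT period.** Section 4.1, under the dose-limiting toxicity heading: "The following events occurring during the DLT observation period (21 days of first cycle) are considered as DLT". The only exemptions are progression and causes obviously unrelated to the study drugs.
- **Evaluability.** Section 4.1 adds: "Any participant who experienced a DLT during the first 21 days will also be DLT-evaluable". Table 14 (section 9.3) otherwise takes "all participants in safety run-in part who have been treated and observed for least 21 days".
- **Cycle length.** Schedule of activities, footnote b: "A treatment cycle is 21 days".
- **Dosing windows.** The schedule of activities shows ±3 days at Cycle 2 Day 1. Section 6.5.2 allows ±3 "days for each of the Q3W IMP administrations" and ±1 "day for cetuximab administration on Day 8 and Day 15 of each cycle".
- **Run-in-specific rules.** Footnote l: "Visit and assessments on C1D3 are only for participants in the safety run-in". Footnote m limits hospitalization to the run-in. The PK flowchart has "Day 3 sampling only for participants in the safety run-in who have a Day 3 visit". Section 8.2.2 sets denser Cycle 1 Day 1 vital signs for the run-in. None of these changes the Cycle 2 Day 1 window.
- **Use of the count.** DLT counts feed Table 3. The Study Board is guided by that table, may decide otherwise, and also weighs the overall safety data.

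**The concern.** The run-in decides whether 24 µg/kg of SAR444245 is kept in the triplet. A first-cycle DLT rate is easiest to interpret when every participant is observed for the whole period after one dose of SAR444245 and pembrolizumab. The stated dosing window and the stated observation period do not fit together: a site can follow the schedule exactly and redose before first-cycle observation ends.

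The overlap days matter because much of the toxicity of interest is tied to infusion. The substudy defines infusion-related reactions as occurring up to 24 hours after an infusion, and it notes that fever is frequent with IL-2 infusion and may be an early sign of CRS. Grade 3 or higher CRS, hypotension and vascular leak are all DLTs. A second infusion on Day 19 opens a new risk window inside the DLT period, and the text does not settle how an event in that window is to be classified.

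**Working it through.** **1. Day arithmetic.** Take Cycle 1 Day 1 as Day 1.

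- Nominal Cycle 2 Day 1 = 1 + 21 = Day 22.
- Permitted window = 22 ± 3 = Days 19 to 25, which is 7 days.
- DLT period = Days 1 to 21.
- Overlap = Days 19, 20 and 21: 3 of the 7 permitted dosing days, and at most 3/21 = 14% of the DLT period.

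**2. The two readings of the DLT wording.**

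- *Calendar reading* (section 4.1, evaluability sentence): the period is the first 21 days. A qualifying event after a Day 19-21 redose counts, so two-dose toxicity enters a first-cycle count.
- *Cycle reading* (section 4.1, DLT definition): the period belongs to the first cycle and could be taken to end when Cycle 2 starts. A Day 19 redose then leaves Days 1 to 18, which is 18 days of single-dose observation. The participant still meets the 21-day evaluability rule in Table 14.

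**3. How likely is early redosing?** Weekly cetuximab is also due at Cycle 2 Day 1. The previous dose is on Day 15 ± 1, so Day 14 to 16.

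| Cycle 2 Day 1 given on | Days since last cetuximab |
|---|---|
| Day 19 | 3 to 5 |
| Day 20 | 4 to 6 |
| Day 21 | 5 to 7 |

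A full 7-day cetuximab interval is possible only on Day 21 after a Day 14 dose. Days 19 and 20 are allowed but unlikely.

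**4. Reproducing Table 3.** The intervals in section 4.1 were used with a Beta(1,1) prior, the decision going to the interval with the largest unit probability mass. DU was assigned when the posterior probability of a DLT rate above 0.3 exceeded 0.95. The prior and the 0.95 cut-off are assumptions, since section 4.1 does not state them. Every cell of Table 3 is reproduced. De-escalation (D or DU) needs at least 3 DLTs at n = 6 to 8 and at least 4 at n = 9 or 10. One event can matter: at n = 6, 2 DLTs gives S and 3 gives D.

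**5. Effect on the decision under the calendar reading.** The protocol gives neither the share dosed early (f) nor the added DLT risk from the second dose (r), so both are assumed. With true first-dose DLT rate p:

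- q = p + (1 − p) × f × r
- P(de-escalate) = P(Binomial(n, q) ≥ threshold)

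For f = 0.10 and r = 0.05, p = 0.20 gives q = 0.20 + 0.80 × 0.005 = 0.204, and p = 0.30 gives q = 0.30 + 0.70 × 0.005 = 0.3035. For f = 0.10 and r = 0.10, q is 0.208 and 0.307.

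| p | n | No early dosing | f = 0.10, r = 0.05 | f = 0.10, r = 0.10 |
|---|---|---|---|---|
| 0.20 | 6 | 9.9% | 10.4% (+0.50) | 10.9% (+1.01) |
| 0.20 | 8 | 20.3% | 21.2% (+0.89) | 22.1% (+1.79) |
| 0.20 | 10 | 12.1% | 12.8% (+0.72) | 13.5% (+1.45) |
| 0.30 | 6 | 25.6% | 26.2% (+0.65) | 26.9% (+1.31) |
| 0.30 | 8 | 44.8% | 45.7% (+0.89) | 46.6% (+1.78) |
| 0.30 | 10 | 35.0% | 36.0% (+0.94) | 36.9% (+1.88) |

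Changes are in percentage points. The table applies Table 3 mechanically, before any Study Board judgement.

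**6. After the change.** A 0/+3 window permits Days 22 to 25, none of which lies in Days 1 to 21.

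**The case against.** The strongest objection is that the master protocol is not shown. The A2 substudy refers to it for IMP administration and for therapy details common to all cohorts. It may well contain run-in rules: the B1 and B2 vital-sign sections mention participants outside the safety run-in, although neither substudy describes one. This stands. A redosing restriction there would resolve the point. Against it, A2 sets its own DLT rules, evaluability definition, schedule and treatment window, and the gap lies between those.

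A second objection is that existing controls suffice. Results are reviewed before each dose, and Grade 3 or higher related events generally require delay or omission. These controls help participants who already have toxicity. They do nothing for one who is well on Day 19, since nothing shown requires the DLT assessment to be complete before the second dose.

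A third is that the numerical effect is slight and the inputs assumed. That is correct, and it is why the point is minor.

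Three stronger inferences are not supported:

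- *That an event after an early second dose definitely counts as a DLT.* The evaluability sentence favours counting it, but the DLT definition can be read as stopping when Cycle 2 begins.
- *That 14% of the DLT period is typically contaminated.* That is a ceiling for a Day 19 redose, and cetuximab timing makes Days 19 and 20 unlikely.
- *That the dose decision is unsound.* Under the calendar reading the error over-counts toxicity, which is the cautious direction. The Study Board can see that an event followed dose 2 and may depart from Table 3.

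**Conclusion.** The point holds as a minor one. In the text shown, the Cycle 2 Day 1 window permits redosing with SAR444245 and pembrolizumab on Days 19-21, and the 21-day DLT period is not protected against it. The consequence depends on which reading applies: second-dose events in the Table 3 count, or as few as 18 days of single-dose observation in a participant still treated as evaluable.

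The effect on the dose decision is small: under 1 percentage point with 10% dosed early and 5% added risk, and 1.0 to 1.9 points with 10% added risk. These figures rest on assumed inputs and cover only the calendar reading. The conclusion also assumes that the master protocol contains no redosing restriction. The case for acting is that the inconsistency is clear and can be removed at almost no cost, not that the run-in would otherwise mislead.

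**What to change.** First check the master protocol. If it does not already prevent redosing before Day 22 in the run-in, make three changes to the A2 substudy:

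1. **Schedule of activities:** add a footnote setting the Cycle 2 Day 1 window to 0/+3 days for safety run-in participants only.
2. **Section 6.5.2:** add a clause that, in the run-in, no Cycle 2 dose of SAR444245 or pembrolizumab is given before Day 22. Keep ±3 days for everyone else.
3. **Section 4.1:** add a sentence that, if a participant is redosed early in error, qualifying events through Day 21 still count in Table 3 and are flagged to the Study Board as following the second dose. This settles the two readings and avoids dropping events.

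The cost is up to 3 days' less scheduling flexibility at one visit for about 6 to 10 participants, and the same again if the run-in is repeated at a lower dose. Sample size and the Table 3 rules are unchanged.

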**Hematologic abnormalities:**

- Grade 4 neutropenia for ≥7 consecutive days
- Grade 3 or 4 neutropenia complicated by fever (temperature of >38.3°C [101°F] or a sustained temperature of ≥38.0°C [100.4°F] for more than 1 hour) or microbiologically or radiographically documented infection.
- Grade 3 or 4 thrombocytopenia associated with clinically significant bleeding requiring clinical intervention.

### **Non-hematologic abnormalities:**

- Grade 3 or above alanine aminotransferase (ALT) or aspartate aminotransferase (AST) in combination with a bilirubin >2 times upper limit of normal (ULN) with no evidence of cholestasis or another cause such as viral infection or other drugs
- Grade 3 or above Vascular Leak Syndrome (VLS)
- Grade 3 or above hypotension
- Grade 3 or above cytokine release syndrome
- Other Grade 3 or above AE except:
  - Grade 3 fatigue that resolves within 1 week
  - Grade 3 nausea, vomiting, or diarrhea that resolves within 72 hours with antiemetics and standard supportive care measures
- Any Grade 3 non-hematologic laboratory value

#### Exceptions:

- Grade 3 electrolyte abnormalities that are not clinically complicated and resolve within 72 hours with conventional medical interventions.
- Grade 3 amylase or lipase that is not associated with symptoms or clinical manifestations of pancreatitis.
- Any Grade 4 non-hematologic laboratory value.

### **Other abnormalities:**

- Any death not clearly due to the underlying disease or extraneous causes.
- Any toxicity requiring permanent discontinuation of the study drug(s).
- More than 1 missing dose of cetuximab due to toxicity.

Participants who are treated at the confirmed safe dose in the safety run-in of Cohort A2 will be included in the total number of participants for Cohort A2.

Please refer to the master protocol for a full description of the study design and for therapy details applicable to all cohorts.

